2 \* Discuss the research design including but not limited to such issues as: probability of group assignment, potential for subject to be randomized to placebo group, use of control subjects, etc.:

This is a pilot randomized controlled trial. Participants will be randomized 1:1, intervention: control. Therefore, there is a 50% chance of any given participant to be in the control group, and a 50% chance of any given participant to be in the intervention group.

3 \* Describe the relevant prior experience and gaps in current knowledge. Describe any relevant preliminary data:

Cancer-related fatigue is a prevalent symptom of cancer and side effect of treatment that can be severe and persistent for years into survivorship. The etiology and pathophysiology of cancer-related fatigue are not well understood [1], though metabolic and circadian processes have been suggested to contribute to its severity. Cancer and cancer treatment, specifically chemotherapy [2-4], disrupts circadian rhythm. Environmental signals that regulate circadian rhythm, or 'zeitgebers' include physical activity, light, and food intake. Several studies have used bright light therapy to entrain circadian processes and have shown positive effects on fatigue among cancer survivors [5, 6]. Also, there is emerging evidence that time-restricted eating can entrain circadian rhythm, but not yet in the cancer population [7]. However, there have been no studies, to our knowledge, that test the ability of time-restricted eating to address cancer-related fatigue.

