## Sample Size and Data Analysis

If you uploaded a separate research protocol document in the 'Research Protocol' page, cite the applicable section and page numbers from that document in the answer boxes below.

1 \* Provide the rationale and sample size calculations for the proposed target population:

This is a two-arm pilot randomized controlled trial that will assess the feasibility of recruitment and retention to a 12-week TRE trial facilitated by the myCircadianClock app as well as the preliminary efficacy of TRE vs. a control arm on the treatment of cancer-related fatigue.

It is common that single-arm pilot studies implementing dietary interventions recruit 10-40 participants (e.g., TRE study among overweight older adults, n=10; ketogenic diet among patients with recurrent glioblastoma, n=20; lifestyle intervention including diet among overweight breast cancer survivors, n=14). In total, 30 participants will be recruited, and approximately 10-20% attrition is anticipated, providing evaluable data from approximately 25 participants. We had more dropouts than anticipated and are upping our sample size to 50 participants so that we can have about 25 participants with evaluable data.

2 \* Provide the plan for data analysis. Include in the description the types of comparisons that are planned (e.g., comparison of means, comparison of proportions, regressions, analysis of variance, etc.), which is the primary comparison/analysis, and how the analyses proposed will relate to the primary purposes of the study:

We will conduct an interim analysis of feasibility after 10 participants have been enrolled. If any unanticipated barriers arise in regard to feasibility of recruitment, data collection, and/or retention, logistical changes will be made to the protocol as appropriate.

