Aim 1 assesses the feasibility of time-restricted eating over 12 weeks. We will note how many people we can screen; how many we can approach; how many are eligible; how many consent; and what percentage provide evaluable data at baseline and 12 weeks. Using data from myCircadianClock, we will extract how many days the participants ate within a 10-h window and the average length of the eating window at baseline, week 6, and week 12. We will consider a participant "adherent" if they ate within the 10-h window at least 80% of days. This goal is based on prior TRE studies. In regard to retention, it is hypothesized that at least 80% (24 out of 30) of those who provide baseline data also provide data at 12 weeks; this goal is based on colleagues' prior behavioral intervention studies with supportive care outcomes.

Aim 2 aims to provide estimates of efficacy comparing time-restricted eating vs. control on fatigue. Linear mixed models (LMMs) for longitudinal data will be used to assess the intervention effect on continuous outcomes (e.g., fatigue) accounting for correlations between the repeated measures. Generalized Linear Mixed Model (GLMM) analyses will be conducted to assess the effect of the intervention on count outcomes. The fixed effects included in the models will be treatment group (TRE versus control), time (baseline, 6 and 12 weeks), group-by-time interaction term and relevant covariates. Random effects will include individual patients. The hypotheses will be tested by evaluating the interaction term of group and time (i.e., 12 weeks). The results of the analyses together with the mean and SD of FACIT-F values as well as change scores will be used in planning future RCTs. All hypothesis testing will be at the two-sided level of 0.05. Following the intent-to-treat principle, all participants will be analyzed as randomized, regardless of their adherence with the intervention.

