### Quality control

Electronic forms will be used and our database will be checked for appropriateness by the study team. All data will be visually inspected. For exploratory measures, if distributional assumptions are not met (e.g., normality of residuals), transformations or nonparametric methods will be used. Outliers will be closely examined to determine if they are erroneous; if they are valid, sensitivity analyses (with and without outliers) will be used. Hypothesis testing will use  $\alpha=0.10$  (two-tailed). The study team will work closely with [name] and his biostatistics team at ICTR.

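### The Aim 2 linear mixed model names a patient random effect but no residual covariance; read as a random intercept, its 5% week 12 test could run at about 6-11% if correlation falls with time

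*Combined protocol and SAP*

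**What the plan says.** In Sample Size and Data Analysis, item 2, the Aim 2 paragraph specifies a linear mixed model for continuous outcomes such as fatigue, "accounting for correlations between the repeated measures". The fixed effects are treatment group, "time (baseline, 6 and 12 weeks), group-by-time interaction term and relevant covariates". On dependence within a patient it adds only: "Random effects will include individual patients". The same sentence also supplies the random effect for the generalized linear mixed model for count outcomes.

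The test is stated as "The hypotheses will be tested by evaluating the interaction term of group and time (i.e., 12 weeks", and "All hypothesis testing will be at the two-sided level of 0.05". Allocation is 1:1. On numbers, the plan is "upping our sample size to 50 participants so that we can have about 25 participants with evaluable data".

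The Quality control and Missing data paragraphs do not fill the gap. The distributional checks are for exploratory measures and give normality of residuals as the example. The missing-data text does not mention covariance structure.

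**The concern.** A random intercept with independent residuals assumes the same variance at every visit and the same correlation for baseline to week 6, week 6 to week 12, and baseline to week 12. The Aim 2 test uses only the last of these pairs. Its model-based standard error, however, comes from a single residual variance averaged over all three.

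If scores 12 weeks apart agree less well than scores 6 weeks apart, the average understates the variance of the tested contrast. The interval is then too narrow and the p-value too small. This interval is the trial's efficacy output, and the plan says the results will be used to plan later randomized trials. The mechanistic aims use the same approach, so any of those outcomes measured at all three visits inherits the question.

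**Working it through.** **Inputs from the documents.** Two-sided 0.05, three visits, week 12 versus baseline contrast, 1:1 allocation, 50 enrolled and about 25 evaluable (half lost).

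**Inputs not in the documents.** The 6- and 12-week correlations. The only related data are from the two-week single-arm pilot (Justification, Objective, & Research Design, item 3): fatigue subscale change 5.3, SD 8.1, effect size 0.55. If that effect size is change divided by the raw SD, and variances are equal, then SD = 5.3/0.55 = 9.64 and the two-week correlation is 1 − 8.1²/(2 × 9.64²) = 0.65. The longer-gap correlations below are assumptions.

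**Formula** (complete data, equal variances σ², no covariates). Let r01, r12 and r02 be the correlations for baseline to week 6, week 6 to week 12 and baseline to week 12, and r̄ their mean.

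- True variance of the contrast: 2σ²(1 − r02)(1/n1 + 1/n2).
- Variance reported by the random-intercept model: 2σ²(1 − r̄)(1/n1 + 1/n2).
- k = (1 − r02)/(1 − r̄); ratio of reported to true standard error = 1/√k; actual level = 2[1 − Φ(1.96/√k)].

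**The plan's own figure.** With equal correlations k = 1 and the level is 5.0%, as stated.

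**Worked case.** For 0.65/0.65/0.50: r̄ = 0.60, k = 0.50/0.40 = 1.25, ratio 0.894, 1.96 × 0.894 = 1.753, level 8.0%.

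**Range, with a check by simulation.** The simulation fitted the random-intercept model by REML to 3,000 null data sets per case, with a t reference. It used 24 complete patients, and 50 enrolled with a quarter lost before week 6 and another quarter before week 12.

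| r01 / r12 / r02 | k | SE ratio | Level, formula | 24 complete | 50, half lost |
|---|---|---|---|---|---|
| 0.6 / 0.6 / 0.6 | 1.000 | 1.000 | 5.0% | 5.0% | 5.0% |
| 0.6 / 0.6 / 0.55 | 1.080 | 0.962 | 5.9% | 5.4% | 5.8% |
| 0.6 / 0.6 / 0.5 | 1.154 | 0.931 | 6.8% | 6.6% | 7.3% |
| 0.7 / 0.7 / 0.6 | 1.200 | 0.913 | 7.4% | 7.8% | 6.7% |
| 0.7 / 0.7 / 0.49 | 1.378 | 0.852 | 9.5% | 9.5% | 9.4% |
| 0.8 / 0.8 / 0.64 | 1.421 | 0.839 | 10.0% | 10.0% | 10.5% |
| 0.8 / 0.8 / 0.6 | 1.500 | 0.816 | 11.0% | not run | not run |

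Monte Carlo error near 5% is √(0.05 × 0.95/3000) = 0.4 points. With a normal instead of a t reference, the equal-correlation case gave 5.8% and 5.6%, so the unstated degrees-of-freedom method also matters a little.

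**Autoregressive decay.** With r12 = r01 = r and r02 = r², k reduces to 3(1 + r)/(3 + r). For r = 0.3, 0.5, 0.7 and 0.9 the level is 7.1%, 8.4%, 9.5% and 10.5%. As r approaches 1, k approaches 1.5 and the level 11.0%.

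**After the fix.** On complete data an unstructured covariance gives the t-test on baseline to week 12 change. That held 4.6-5.4% across the simulated cases. With half lost, a complete-case change t-test gave 4.5-5.6%. A separate run of 600 replicates (25 per arm, 70% observed at week 6 and 50% at week 12) fitted the unstructured model itself. It gave 4.0-6.7%, with Monte Carlo error √(0.05 × 0.95/600) = 0.9 points, and about a 2% larger standard error when equal correlation was true. That run used completers minus 2 as degrees of freedom; Kenward-Roger was not simulated.

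**The case against.** **The text does not say random intercept only.** It says random effects will include patients, in a model meant to account for correlation. A reader might infer that the plan forces equal correlation. It does not: a slope or a structured residual covariance is not excluded. What stands is that no structure is specified, and that the one effect named gives equal correlation by default.

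**The size rests on assumed correlations.** This is right. A reader might infer that the false-positive rate is above 5% as the plan is written, or that any weakening gives 7% or more. Neither follows: equal correlations give 5.0%, and a drop of 0.05 gives about 6%. The pilot value does not settle it. Exponential decay from 0.65 at two weeks gives 0.65³ = 0.27 at six weeks, k = 3 × 1.27/3.27 = 1.165 and a level of 6.9%, towards the lower end. Nor does the entry criterion show a narrowed baseline spread on the outcome: it is a single 0-10 worst-fatigue item, not the FACIT-F subscale.

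**The consequence is modest.** Aim 2 estimates preliminary efficacy in a pilot. Planning will also use raw means, SDs and change scores, which do not depend on the model's covariance, and with complete data the point estimate is unchanged. This limits the weight of the point but does not remove it.

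**Not every outcome is affected.** A reader might extend the point to glucose. The mechanistic paragraph lists glucose at baseline and week 12 only, and with two visits there is a single correlation and no problem. Study Procedures (Continuous glucose monitoring) adds week 6, so the two sections differ. The Quality control paragraph also gives a two-tailed 0.10, apparently for exploratory measures, so the 5% figures here are for Aim 2.

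**Conclusion.** The point holds as a gap in specification with a conditional consequence. The covariance structure of the Aim 2 linear mixed model is not stated, and the natural reading is a random intercept.

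Under that reading, with equal variances and no covariates, the week 12 test keeps its 5% level if the three correlations are equal. It becomes too liberal when the baseline to week 12 correlation is below the average of the three. For assumed drops of 0.05 to 0.2, or autoregressive decay with a 6-week correlation of 0.3 or more, the standard error is about 4-18% too small and the level about 6-11%. This is not an upper bound: 0.8/0.8/0.5 gives k = 0.50/0.30 = 1.667, 1.96/√1.667 = 1.518 and a level of 12.9%.

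The change is worth making because it is cheap and standard for three visits, not because inflation has been shown to occur in this trial.

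**What to change.** Keep the patient random effect for the count-outcome generalized linear mixed model; deleting the sentence outright would leave that model with none. For continuous outcomes add:

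> The LMM will use an unstructured residual covariance over the three visits in place of the patient random intercept (REML, Kenward-Roger degrees of freedom). If it does not converge, a prespecified simpler structure with robust (sandwich), small-sample-corrected standard errors will be used.

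Name the simpler structure in the plan. A heterogeneous Toeplitz structure would help little, since at three visits it has five parameters against six. Keep the fixed effects and the week 12 contrast as they are. Reconcile the two sections on whether glucose is measured at week 6, since an outcome measured only at baseline and week 12 does not need the change.

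Cost: a few lines of wording and no new data. The model estimates six covariance parameters (three variances, three correlations) instead of two, and the interval may be wider. Where equal correlation is in fact true, the loss was about 2% in standard error in the cases tried.

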The first aim of our project is to test whether we are able to deliver a 12-week time-restricted eating program. The second aim is see if participants in the time-restricted eating group have less fatigue at week 12 compared to those in the control group, taking into account their fatigue at the beginning of the study. To look more closely at the biology and physiology underlying fatigue, we will measure circadian rhythm at the beginning, the middle (week 6), and the end of the study (week 12) using a wrist-worn actigraph (like a Fitbit or Apple Watch), as well as sugar metabolism using a continuous glucose monitor (nonintrusive device that sticks to the back of the upper arm). We hypothesize that time-restricted eating will lead to less fatigue, a stronger circadian rhythm, and healthier sugar metabolism.

ID: VIEW4E92805CF7000  
Name: v2\_Lay Summary

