## Justification, Objective, & Research Design

If you uploaded a separate research protocol document in the 'Research Protocol' page, cite the applicable section and page numbers from that document in the answer boxes below.

1 \* Describe the purpose, specific aims, or objectives of this research. State the hypothesis to be tested:

This pilot randomized controlled trial will test the effects of time-restricted eating vs. an unrestricted eating pattern (i.e., control) on persistent cancer-related fatigue, circadian rhythm, and metabolism. These data build upon a study conducted by [name] (PI) that established the feasibility and safety of time-restricted eating among cancer survivors—cancer survivors were willing and able to eat within a 10-hour window for 14 days. The specific aims are as follows:

Aim 1: To assess the feasibility of time-restricted eating for 12 weeks, utilization of the myCircadianClock app, continuous interstitial glucose monitoring, and the wrist-worn actigraph. We hypothesize that 80% of participants will provide evaluable data regarding their eating window via the app at baseline and 12 weeks. We also hypothesize that at least 80% of participants who are in the time-restricted eating arm and provide evaluable data will eat within a daily average window that is  $\leq 10$  hours.

Aim 2: To estimate the preliminary efficacy of a 12-week time-restricted eating intervention vs. an unrestricted eating pattern on patient-reported fatigue among fatigued cancer survivors, as measured using the Functional Assessment of Chronic Illness Therapy-Fatigue (FACT-F) questionnaire. We hypothesize that FACT-F fatigue subscale scores will be lower for those in the time-restricted eating group compared to the control group at week 12, controlling for baseline levels.

Mechanistic (exploratory) aims: To assess the effects of a 12-week time-restricted eating intervention vs. an unrestricted eating pattern on circadian rhythm (mesor, amplitude, and acrophase from actigraphy), sleep parameters (e.g., sleep efficiency), and biomarkers of metabolism (fasting blood glucose, glucose excursions).

1. To assess cross-sectional associations between circadian rhythms, metabolism, and fatigue at baseline.
2. To explore associations between changes in circadian rhythms, metabolism, and fatigue from baseline to 6 weeks and baseline to 12 weeks.
3. To explore associations between adherence to the intervention and changes in the same measures.

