Potential participants will be identified using four methods: (i) screening medical records, (ii) direct referral from providers (e.g., nurses, nurse navigators, physicians), (iii) flyers, and (iv) advertising via standard UMB- and ICTR-networks. The study staff will screen for potential participants using EPIC or, alternatively, patients may be referred to the study team by a provider or acquaintance. Initial contact will occur via the following methods: i) the treating oncologist or a member of the medical team (e.g., nurse practitioner) will introduce the study to the participant via a clinic appointment (in person or telehealth) and inquire if it would be okay for our study team to talk with them after their visit or contact them, ii) with approval of the treating oncologist or a designee, a recruitment letter will be sent to the potential participant briefly describing the study and asking them to contact us if they would like more information, and iii) with approval of the treating oncologist or a designee, a message will be sent to the potential participant via MyPortfolio briefly describing the study and asking them to contact us if they would like more information. If a potential participant is interested, the study team will provide more information about the study in-person or via phone.

The study activities are briefly described here; the study schema is illustrated in Figure 1 (see Additional Documents, "schema-data-collection.pdf," page 1).

At baseline, participants will complete an on-study form that includes demographics and clinical characteristics as well as questionnaires (see below). We will obtain a baseline body weight measurement. For one week (week 0), participants will wear an actigraph (i.e., activity tracker) and a continuous glucose monitor and complete a food log using the myCircadianClock app.

After the baseline period, they will be randomized 1:1, TRE:control. Those in the time-restricted eating group will be asked to eat all food and beverages in a self-selected 10-hour window during the day. The start time of the window can be chosen based on the participant's schedule and preferences, but it should be the same for the duration of the study. We will not restrict what people eat. Black coffee and unsweetened tea will be allowed before the window, and water and medications are allowable any time. Those in the control group will be asked to not make any changes to their current dietary patterns.

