**2 \* Describe procedures for orderly termination:**  
Upon completion of data collection and return of the actigraph, each participant will be thanked for their participation in the study and compensated for their time.

If a participant withdraws (or is withdrawn) before the end of the study, they will be paid for the time they spent providing data and the study team will not contact the person anymore. A 10-20% withdraw rate is built into the study design and recruitment goal, so there should not be a need to replace participants who withdraw before completing the study.

**3 \* Describe procedures that will be followed when subjects withdraw from the research, including partial withdrawal from procedures with continued data collection:**  
If a participant wishes to withdraw from the study, we will ask if the participant would like to continue participation in some but not all of the research activities. If they would like to participate in only some of the research activities, we will note which ones and the participant will not be formally withdrawn from the study. If they wish to withdraw completely, a written withdrawal request is required and should be sent to the PI (email preferred). The written request for withdrawal will be included in the participant's study record as documentation of the reason for removing a participant from the study. If a participant makes a verbal request and does not provide a written request, the verbal request will be documented by the study team member who receives the request and added to the participant's study record. Data that have been collected thus far will be analyzed.

ID: VIEW4E1B5251F800  
Name: v2\_Withdrawal of Participants

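### Aim 2 is stated as a baseline-adjusted week 12 difference but tested as a change-from-baseline contrast; both are unbiased, and the planned test may give up a little precision

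*Combined protocol and SAP*

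**What the plan says.** Under Justification, Objective, & Research Design (item 1), Aim 2 predicts the fatigue subscale in the time-restricted eating arm "compared to the control group at week 12, controlling for baseline levels". The Lay Summary describes the same week 12 comparison, "taking into account their fatigue at the beginning of the study".

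Sample Size and Data Analysis (item 2) specifies a linear mixed model: "The fixed effects included in the models will be treatment group (TRE versus control), time (baseline, 6 and 12 weeks"), their interaction and unnamed covariates, with a random effect for patient. The test is given as "The hypotheses will be tested by evaluating the interaction term of group and time (i.e., 12 weeks").

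On who enters the analysis, the same section says "all participants will be analyzed as randomized, regardless of their adherence with the intervention". Study Procedures fixes the order of events: "After the baseline period, they will be randomized 1:1, TRE:control". Enrolment was raised to 50 "so that we can have about 25 participants with evaluable data".

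Nothing in the documents sets the baseline means equal or names baseline fatigue as a covariate.

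**The concern.** With baseline among the outcomes and a free group main effect, the group-by-week-12 coefficient is the week 12 difference minus the baseline difference. The aim describes a week 12 difference adjusted for baseline. Both target the same effect in a randomised trial, but in any one trial they give different numbers, because the first removes the whole of the chance baseline imbalance and the second only the part that predicts week 12.

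Two things are at stake, both modest. The plan leaves open which number is the Aim 2 result. And with about 25 evaluable participants, the estimate that is meant to inform later trials may carry a slightly wider interval than the same data allow. The unnamed covariates do not settle this: baseline fatigue is already an outcome in the model, so it cannot sensibly be added as a covariate too.

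**Working it through.** **Inputs from the documents.** Allocation is 1:1 after baseline. The original sizing gives 30 × (0.8 to 0.9) = 24 to 27 evaluable, which reproduces the stated figure of about 25. The revised sizing, 25 of 50, implies 50% loss. Withdrawal of Participants (item 2) still says "A 10-20% withdraw rate is built into the study design and recruitment goal", which on 50 would leave 40 to 45. The documents do not say when dropouts leave.

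**Assumptions.** Correlation ρ between visits is 0.5, 0.65 or 0.8, equal across visits. Baseline SD is 1 and follow-up SD is k. There are 13 and 12 completers and, in the main case, 12 and 13 people with baseline only, so 25 per arm. The earlier two-week study offers a loose check on ρ. Its change of 5.3 and effect size of 0.55 imply an SD of 5.3/0.55 = 9.6. With a change SD of 8.1, ρ = 1 − 8.1²/(2 × 9.64²) ≈ 0.65. This holds only if that effect size used a raw-score SD that was equal at both times.

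**Formulas (covariance known).**
- Shared baseline mean: S = k²(1 − ρ²)(1/13 + 1/12).
- Planned, half with baseline only: P = S + (1 − kρ)²(1/25 + 1/25).
- Planned, completers only: P = S + (1 − kρ)²(1/13 + 1/12).
- Narrowing of the interval: 1 − √(S/P).

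**Equal variances (k = 1).**

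| ρ | S | P, half baseline-only | Narrower | P, completers only | Narrower |
|---|---|---|---|---|---|
| 0.5 | 0.1202 | 0.1402 | 7.4% | 0.1603 | 13.4% |
| 0.65 | 0.0925 | 0.1023 | 4.9% | 0.1122 | 9.2% |
| 0.8 | 0.0577 | 0.0609 | 2.7% | 0.0641 | 5.1% |

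With the covariance estimated (40,000 simulated trials per case, REML random intercept, 2 × 25 − 4 = 46 df in both models), the mean width falls by 8%, 5% and 3% when half have baseline only, and by 14%, 10% and 6% with completers only. Type I error stays at 4.9-5.3% in both models. If 20% have baseline only, the known-covariance gain is about 4-11%.

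**Unequal variances, half with baseline only.** Example for k = 1.2, ρ = 0.5: S = 1.44 × 0.75 × 0.1603 = 0.1731; P = 0.1731 + (1 − 0.6)² × 0.08 = 0.1859; narrowing 3.5%.

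| k | ρ = 0.5 | ρ = 0.65 | ρ = 0.8 |
|---|---|---|---|
| 1.2 | 3.5% | 1.4% | 0.1% |
| 1.3 | 2.3% | 0.6% | 0.1% |

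**How far the two results can differ.** With k = 1 and half baseline-only, the difference between the two estimates has SD (1 − ρ)√0.08, which is 0.14 outcome SD at ρ = 0.5 and 0.06 at ρ = 0.8.

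**The case against.** The planned model is standard and valid, the aim and the lay summary are not analysis specifications, and ordinary language about taking baseline into account is met by a change contrast. The pilot is sized by precedent and Aim 2 only estimates preliminary efficacy. All of this stands, and it limits the point to efficiency and clarity.

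The weightier objection concerns variance. Eligibility requires a score of 4 or more on worst fatigue, and selection on baseline fatigue can make the baseline spread smaller than the follow-up spread. The screening item is not the outcome scale and no SD ratio is given, but the gain then nearly disappears. A shared baseline mean with a random intercept alone can also mislead. In simulations with half baseline-only and ρ = 0.65, at k = 1.2 the reported interval was 6% narrower while the estimator's true SD was unchanged (ratio 0.999), and type I error rose from 5.3% to 6.7%. At k = 1.3 it rose from 6.0% to 7.9%. This stands too, and it shapes the fix.

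A reader might infer that the planned test is biased or answers a different question. The documents do not support that: randomisation comes after baseline. Informative dropout would be a problem for either version. A reader might also take 3-8% as a property of this trial. It is not, because the correlation, the variances and the timing of dropout are all unstated.

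**Conclusion.** The mismatch between the stated comparison and the tested term is real, and the plan should say which one is the Aim 2 result. The precision given up is conditional and small to moderate: about 3-8% of interval width with equal visit variances, ρ of 0.5-0.8 and half of the 50 contributing baseline only. In that case the variance ratios are worth about 3 to 8 more enrolled participants (50/0.947 = 52.8; 50/0.857 = 58.3).

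It rises to about 5-14% if only completers enter, which would happen if losses precede randomisation or if complete-case results are reported, as the Missing data section permits. It falls to about 0-4%, in the baseline-only case, if follow-up SD is 1.2-1.3 times baseline SD. The planned analysis is not invalid. This is an optional improvement.

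**What to change.** In Sample Size and Data Analysis (item 2), make the baseline-adjusted week 12 difference the single Aim 2 result:

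- Use fixed effects for time, group-by-week-6 and group-by-week-12, with no group effect at baseline, and test the week 12 group term.
- Keep all randomised participants, including those with baseline only.
- Allow the variance to differ between baseline and follow-up and do not rely on a random intercept alone. With visit-specific variance, type I error stayed close to that of the planned test (4.5-6.5% against 4.5-6.8%), and a gain remained when the variances were in fact equal.
- Report change scores descriptively, as already intended for planning later trials.

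The cost is one or two sentences and no new data. The gain is modest and may vanish. Two alternatives return most or all of it when half have baseline only. A week 12 ANCOVA in completers (22 df) has width ratios of 0.97, 1.00 and 1.02 against the planned test at ρ = 0.5, 0.65 and 0.8. A fully unstructured covariance costs about the same, because its week 12 estimate then equals that ANCOVA.

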Mechanistic exploratory aims will be evaluated using the same analytical approach as for the primary aim. For circadian rhythm, we will use actigraphy and patient-reported myCircadianClock app data to measure objective symptoms of sleep quality. We can use the actigraph to assess activity in three axes, recorded as "counts." Counts are used to calculate the strength of circadian rhythms as well as deduce active periods and sleep measures (i.e., sleep latency, sleep efficiency, sleep duration, wake after sleep onset, daytime napping). To evaluate circadian activity, we will use a two-oscillator (12 and 24 hours) cosinor model to estimate key circadian rhythm parameters. Also at baseline and week 12, we will assess interstitial glucose concentrations using a continuous glucose monitor. From these data we will extract fasting glucose, average daily glucose, average waking and nocturnal glucose, maximum glucose, and area under the curve. We will explore associations between objective and subjective measures at baseline, adjusting for confounding factors (e.g., age, depression), in addition to changes over time and effects of the intervention on these parameters.

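### The analysis plan sets two significance levels, two-sided 0.05 and two-sided 0.10, without saying which tests each one governs

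*Combined protocol and SAP*

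**What the plan says.** Both statements are current text in the answer to item 2 of Sample Size and Data Analysis.

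- **Aim 2 paragraph.** After describing the mixed model, the plan says "The hypotheses will be tested by evaluating the interaction term of group and time (i.e., 12 weeks", and shortly afterwards "All hypothesis testing will be at the two-sided level of 0.05".
- **Mechanistic aims paragraph.** "Mechanistic exploratory aims will be evaluated using the same analytical approach as for the primary aim". No separate significance level is given.
- **Quality control paragraph.** One sentence concerns exploratory measures: "For exploratory measures, if distributional assumptions are not met (e.g., normality of residuals), transformations or nonparametric methods will be used". A sentence on outliers follows, not limited to exploratory measures. Then comes "Hypothesis testing will use $\alpha=0.10$ (two-tailed".

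Neither alpha statement refers to the other, and neither attaches its level to a named list of endpoints.

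**The concern.** A plan has to fix the rejection threshold before the data are seen. This one gives two, both two-sided and both in general terms. Whoever writes the primary paper can cite either sentence, and nothing stops that choice being made after the p-value is known. Choosing the more lenient level once p is known has the same effect as testing at 0.10 throughout, which doubles the nominal false-positive rate from 5% to 10%.

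The threshold has work to do here. The protocol states a directional fatigue hypothesis for Aim 2, commits to testing it, and plans a primary-aims publication and a follow-on trial. The study is open label, and the principal investigator takes part in data acquisition unblinded, which is a further reason to leave no analytic choice open.

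**Working it through.** **1. Can the two levels be reconciled?**

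- Two-sided 0.05: critical |z| = 1.960.
- Two-sided 0.10: critical |z| = 1.645.

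A two-sided 0.10 test has the same upper critical value as a one-sided 0.05 test. That does not help, because the 0.05 sentence says two-sided. The levels differ by a factor of two. Any result with |z| between 1.645 and 1.960 gets opposite verdicts. Under the null hypothesis that happens with probability 0.10 − 0.05 = 5% per test.

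**2. Does the 0.10 sentence have a limited scope?**

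The reference to exploratory measures opens and governs one sentence, on distributional assumptions. The outlier sentence after it is general, and the alpha sentence after that carries no qualifier. The mechanistic paragraph ties those aims to the primary approach and gives no alpha of its own. So the text does not confine 0.10 to exploratory outcomes. If it did, the Aim 2 sentence would still claim every test for 0.05.

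**3. Is there a design figure to reproduce?**

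No. The plan reports no power calculation. Its only sample-size arithmetic concerns attrition: 30 × 0.9 = 27 and 30 × 0.8 = 24, in line with about 25 evaluable. The revised target is described as "upping our sample size to 50 participants so that we can have about 25 participants with evaluable data", which implies a loss of 1 − 25/50 = 50%. Neither figure uses alpha.

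**4. How often would the choice decide the verdict? (illustration)**

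Inputs:

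- About 25 evaluable in total (Sample Size and Data Analysis) and 1:1 allocation (Justification, Objective, & Research Design), taken as 13 versus 12.
- Standardised effect d = 0.55, the effect size reported for the FACT-F fatigue subscale in the single-arm feasibility study. Using it as a between-arm effect is an assumption, and probably an optimistic one.
- A two-sample t-test as a stand-in for the planned mixed model.

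With 23 degrees of freedom the critical t is 2.069 at 0.05 and 1.714 at 0.10. The noncentrality parameter is d / √(1/13 + 1/12) = 0.55 / 0.4003 = 1.374. Power is P(|T| > critical t) under the noncentral t distribution. The same calculation at other assumed effects gives:

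| Assumed d | n per arm | Power at 0.05 | Power at 0.10 | Verdict depends on level |
|---|---|---|---|---|
| 0.20 | 13 / 12 | 7.7% | 14.0% | 6.3% |
| 0.30 | 13 / 12 | 11.1% | 18.8% | 7.7% |
| 0.55 | 13 / 12 | 26.1% | 37.9% | 11.8% |
| 0.65 (= 5.3 / 8.1) | 13 / 12 | 34.7% | 47.7% | 13.0% |
| 0.55 | 25 / 25 | 47.8% | 60.7% | 12.9% |

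The 0.65 row uses the feasibility study's mean change of 5.3 and SD of 8.1 directly. The last row is an upper bound in which all 50 enrolled participants contribute. The plan itself expects about half of that.

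**5. The same gap in fatigue points.**

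With SD 8.1, the standard error of the difference is 8.1 × 0.4003 = 3.243. The smallest observed difference called significant is 2.069 × 3.243 = 6.7 points at 0.05 and 1.714 × 3.243 = 5.6 points at 0.10. The feasibility study's 5.3-point change lies just below that band, so a result inside it is realistic.

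**The case against.** The best defence is that each sentence is local to its paragraph. On that reading, the 0.05 sentence covers all testing within Aim 2, the 0.10 sentence covers the exploratory measures mentioned just before it, and the fatigue test stays at 0.05. This may be what the authors intended. It is not what they wrote: the first sentence is universal, the second is unqualified, and the mechanistic aims are told to follow the primary approach. What stands is that the threat to the fatigue test's error rate is conditional. It arises on the unrestricted reading. On the local reading the conflict touches only hypothesis-generating tests.

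A second defence is that this is a pilot. Aim 1 is feasibility and Aim 2 is framed as estimation to plan later trials. The sample size does not rest on alpha, and no stopping or progression rule uses a p-value. That is correct and it limits the damage: point estimates do not change with alpha, only the significance label and any confidence level matched to it. It does not remove the error, because the plan still commits to hypothesis tests that will be reported.

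It is also fair to say that the contradiction alone does not show which level was intended, and that the power figures rest on an effect size taken from a two-week, uncontrolled, before-and-after comparison.

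**Conclusion.** The concern holds. The plan gives two incompatible two-sided levels in one analysis section, and no reading of the current wording makes both sentences true. This conclusion rests on the text alone.

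Its size depends on scope. On the unrestricted reading, the type I error of the Aim 2 fatigue test is left between 5% and 10%. On the exploratory-only reading, the same ambiguity applies to the mechanistic tests. With about 25 evaluable participants, the chance that a verdict turns on the choice is 5% under the null and about 6% to 13% over assumed standardised effects of 0.20 to 0.65, with about 12% at 0.55. These percentages are illustrations from a t-test on assumed effects, not figures from the plan. The sample size and the Aim 1 feasibility targets are unaffected.

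**What to change.** State one level for each named set of tests, and do so before the outcome data are analysed.

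- **Fatigue test.** Keep two-sided 0.05 for the Aim 2 group-by-time comparison at 12 weeks, as its own paragraph says, and report the estimate with a 95% confidence interval. The interval is an addition, in keeping with the aim of estimation.
- **The 0.10 sentence.** Delete it from Quality control. If it was meant for the mechanistic outcomes, restrict it there to exploratory mechanistic outcomes, labelled hypothesis-generating, and reword the Aim 2 sentence so that it refers to the Aim 2 hypothesis test and not to every test.

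Deletion changes one sentence and the second option changes two. Neither needs new data, a new sample size or any change to study conduct.
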